ID: Pro00103863

Identifying the Optimal Neural Target for Misophonia Interventions

NCT04348591

Study protocol and statistical analysis plan

3/28/2023

Methods:

1. Participants and Procedures

This study was pre-registered under the Clinical Trials ID (NCT04348591) and ran between October 2020 and May 2022. The study was powered based on expected effect size derived from Kumar et al. [2], who compared misophonic participants ($n = 20$) with controls ($n = 22$) to find significant differences in AIC response, with an effect size of 1.27 (mean difference between groups = 2.7 a.u, $SD = 2.11$). For the proposed design, with planned comparisons across condition (downregulate, or listen), sound type (misophonic, aversive, or neutral) and group (misophonic vs. clinical control), and an expected effect size of 1.27, and alpha error rate set at .05, we expected adequate power (over 80%) with 29 participants in each group. Therefore, we aimed to recruit 30 participants in each condition.

Participants were recruited through online websites (e.g., Craigslist, Dukelist), social media (Facebook, Reddit), flyers, and electronic medical record outreach. Participants reached the study predominantly by seeing advertisements on social media and research websites. Many participants who met the severity cutoff for misophonia also found the study via self-guided internet search (see Table 1 for how participants who met the cutoff for each group of interest for the study found the study information).

Table 1. Recruitment methods and success rate in identifying the groups of interest for the study

Recruitment material used	Misophonia participants	Emotion dysregulation participants
Social media (Facebook, Reddit, Instagram)	33.46%	36.42%
Websites (Dukelist, Dukescience, Duke Misophonia website, Dukehealth)	30.08%	28.90%
Word of mouth (friend or medical professional referral)	13.16%	9.83%
Self-guided internet search (including finding the study on clinicaltrials.gov)	12.78%	13.29%
Volunteer registries (BIAC, ResearchMatch, CMER)	6.39%	6.36%
Outreach using electronic medical record	3.38%	4.62%
Newspaper	0.75%	0.58%

Note. Participants were included in the misophonic group if they scored ≥ 2 on the MQ subscales and indicated a severity higher than 6 on the MQ severity scale; participants were included in the emotion dysregulation group if they scored above 89 on the DERS scale.

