One hundred and twelve unique adults signed consent and participated in an in person screen to establish diagnostic profile, and examine any remaining inclusion/exclusion criteria (See Figure 1 for a visual depiction of the study design). We repeated the MQ and DERS at the in person screen and only

[figure not shown]

Figure 1. Experimental design

allowed participants in the study if the scales scores fit within our pre-determined parameters at the intake assessment. Twenty-two participants were no longer eligible at intake because their MQ and DERS scores changed sufficiently to be outside of the pre-determined cutoffs for the misophonic/clinical control groups. In addition, 19 participants were not eligible at the in person screen (see CONSORT) and 12 withdrew, were lost to contact before the experimental day, or couldn't do the MRI visit because of claustrophobia or technical difficulties. Thus, we had 59 enrolled participants for the study (enrolled group) of which 54 participants (completer group) were present for the neurostimulation experimental day (27 in each group).

Enrolled participants were 4 men and 52 women and 3 non-binary adults between the ages of 18 and 54 ($M = 28.31$; $SD = 9.06$ years old) who self-reported significant misophonic severity, or who met

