regressors: [listen to misophonic vs. aversive sounds], [downregulate vs. listen to misophonic sounds], [listen to aversive vs. neutral sounds], and [downregulate vs. listen to aversive sounds]. For all, the PPI was defined as the interaction between this event and the physiological regressor (66, 67). This method was performed for each subject and for each run. A third level analysis was then performed to assess the differences between groups. PPI analyses probe the synchronization of brain activity between two brain regions allowing us to differentiate regions which interact with each other versus work independently during experimental tasks (68). Whole brain Z image statistics (from both functional and PPI analyses) were thresholded using clusters determined by $Z > 2.3$ and a corrected cluster significance of $p = .05$ (69). Mixed-effects hierarchical linear models (MMANOVA) with analytically determined covariance structures were used to analyze the repeated measures data (70). All MMANOVA models used a restricted estimated maximum likelihood model to account for missing data (71) (i.e., cases with missing data were not discarded, but slopes for each participant were computed with the data available). Estimated marginal means (EMMs) were compared using LSD corrections for significant main and interaction effects, and are presented in the results section. For data that was not repeated, independent sample t -tests or non-parametric equivalents were employed. To test the neurobiological basis of misophonia, correlation analyses with neuroimaging data extracted from regions of interest (ROIs) and baseline behavioral measures were employed.

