To compare the effects our neurostimulation conditions, we conducted four analyses examining SUDS, peak GSR (SCR; peak arousal), SCL (tonic arousal), and HF-HRV. For the SUDS analyses, we examined the difference between SUDS at the end of each sound and the baseline SUDS collected after the task baseline. If task baseline SUDS were missing, session baseline SUDS were utilized instead. For the SCR analysis, the maximum value of the GSR during the presentation of each sound was used as outcome. For those two variables, the experimental group was used as a between-subject variable (misophonic or emotion dysregulation), and the experimental neurostimulation condition (active HF-rTMS over the right DLPFC, active LF-rTMS over the mPFC- insula, sham rTMS), the block instruction (downregulate misophonic, downregulate aversive, hear misophonic, hear aversive, hear neutral), the order effect of the 3 neurostimulation condition time within the task (0-2, corresponding with the runs employed), within the run (0-4, corresponding to each block), and within the block (0-3, corresponding to each of the sounds played), were used a within-subject variable. The experimental group by neurostimulation condition by block instruction interactions were entered as effects in the SUDS and SCR analyses. For SCR, the maximum GSR value during the habituation period was also controlled for. For the SCL and HF-HRV analyses, the experimental group and neurostimulation condition, and block instruction were also used but only the average within each block was used as outcome, time within block was excluded because HF-HRV requires at least 120s to be accurately assessed, and baseline values were added as main effects, time was considered a categorical variable. To account for multiple comparisons, we used a Bonferroni correction, and dropped the significance threshold to .0125. Differences between LF and HF rTMS were not hypothesized, but explored where both stimulation conditions were different than sham.

Planned covariates for all analyses included coil-to-cortex distance- given evidence that higher distance may impede the effectiveness of neurostimulation interventions for emotion regulation that are not designed to account for this parameter [77,78] - and data-driven covariates were also examined and added to these analyses as needed. Effect sizes were computed by using Feingold's formula [79] and interpreted using Cohen's specifications [80].

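### LSD leaves the follow-up contrasts unadjusted, and the .0125 threshold does not make up for this in the block-instruction pairs or the cell-level interaction contrasts

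*Combined protocol and SAP*

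**What the plan says.** Everything on this point is in section 7 (Statistical Analyses) of the combined protocol and SAP.

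- **Post hoc step:** "Estimated marginal means (EMMs) were compared using LSD corrections for significant main and interaction effects".
- **Outcome analyses:** "we conducted four analyses examining SUDS, peak GSR (SCR; peak arousal), SCL (tonic arousal), and HF-HRV".
- **Threshold, stated after those analyses are described:** "we used a Bonferroni correction, and dropped the significance threshold to .0125". The divisor is not given.
- **Factors:** group has two levels and stimulation has three (HF over dlPFC, LF over mPFC, sham). The third factor is "the block instruction (downregulate misophonic, downregulate aversive, hear misophonic, hear aversive, hear neutral", which has five levels.
- **Interaction:** "The experimental group by neurostimulation condition by block instruction interactions were entered as effects in the SUDS and SCR analyses". For SCL and HF-HRV the same factors are named but no interaction is stated.
- **Comparison of the two active conditions:** "Differences between LF and HF rTMS were not hypothesized, but explored where both stimulation conditions were different than sham".

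The plan does not say whether .0125 applies to the omnibus tests, the marginal-mean contrasts or both. It does not list the contrasts to be examined. Section 1 gives the sample: "54 participants (completer group) were present for the neurostimulation experimental day (27 in each group". It also says the study "ran between October 2020 and May 2022", while the document is dated March 2023.

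**The concern.** Calling LSD a correction suggests that the contrasts are adjusted for their number. They are not: each pairwise p-value is an ordinary t test. A significant omnibus test guards against false contrasts when nothing differs. Once a real effect makes that test significant, every remaining null contrast in the family is tested at the full threshold.

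The trial asks which stimulation target works. If a significant interaction is followed up cell by cell, statements that a target beats sham in a given group under a given instruction rest on these tests. Some errors would credit a target that does nothing. Others would credit the working target in the wrong group or under the wrong instruction. A false active-versus-sham result can also help to open the LF versus HF comparison. GSR change is among the outcomes set a priori as primary; SUDS is secondary.

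**Working it through.** **1. The plan's threshold.** .05/4 = .0125, and 4 × .0125 = .05. The whole .05 is used across the four outcomes.

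**2. Size of the families.**
- Stimulation main effect: 3 × 2/2 = 3 pairs.
- Block instruction: 5 × 4/2 = 10 pairs.
- Three-way interaction: 2 × 3 × 5 = 30 cells, and 2 groups × 5 instructions × 2 active targets = 20 active-versus-sham contrasts.

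**3. Assumptions that the documents do not give.** Two-sided tests; normal, independent, equal-variance cells with one value per cell; shifts in cell-SD units; all 20 cell contrasts examined. With 27 per group, the error df are (54 − 2) × 14 = 728. The three-way F test has 1 × 2 × 4 = 8 df and is gated at .0125. Rates below are shares of all trials, including those where the gate stays shut.

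**4. Where the gate is enough.** With no effects, false cell contrasts occur in .009 of trials. For the three-level stimulation effect with one level truly different, one null pair remains. Its error is .012 with contrasts at .0125, and .051 if contrasts are read at .05 behind a .0125 gate.

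**5. Block-instruction pairs.** With one of five levels shifted, 10 − 4 = 6 pairs are null. Six independent tests would give 1 − (1 − .0125)^6 = .073. The pairs share means, so simulation gives less: .056 at 0.3 SD and .061 at 0.5 SD, over four times the .0125 share.

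**6. Cell contrasts behind the three-way gate.** For one shifted cell, the noncentrality of the three-way F is 27 × d² × (1/2)(2/3)(4/5) = 7.2 d².

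| One cell shifted by (SD) | 0.5 | 0.8 | 1.0 | 1.5 |
|---|---|---|---|---|
| Gate opens | .041 | .123 | .231 | .664 |
| Any false contrast, tests at .0125 | .021 | .046 | .074 | .155 |
| Same, run-level SD equal to cell SD | .013 | .031 | .053 | .124 |
| Any false contrast, tests at .05 | .037 | .099 | .171 | .423 |

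At .0125, a false contrast for the ineffective target occurs in 1/3/4/9% of trials. One for the effective target in a wrong cell occurs in 1/3/4/8%; the two overlap.

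In a crossover, one target shifts by +d in one group and −d in the other under two instructions. Noncentrality is 27 × d² × 2 × (2/3) × (6/5) = 43.2 d².

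| Crossover, d (SD) | 0.5 | 0.8 | 1.0 |
|---|---|---|---|
| Gate opens | .412 | .938 | .997 |
| Any false contrast, tests at .0125 | .096 | .168 | .176 |
| Same, run-level SD equal to cell SD | .073 | .144 | .153 |

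**7. Patterns that do not inflate the error by this route.** If a target shifts all ten of its cells equally, or only the downregulate blocks of both groups, the three-way noncentrality is zero. The gate then opens in about 1.2–1.3% of trials, and false cell contrasts through it stay below 1%.

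**8. Holm with the gate kept.** Holm over the 20 cell contrasts at .0125 starts at .0125/20 = .000625. Behind the gate it held error at .012 or below. Over the ten block pairs it starts at .0125/10 = .00125, with simulated error of .008–.010 (run without the gate).

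**The case against.** **The main question is protected.** Gated LSD is sufficient for active versus sham pooled over groups and instructions, provided the contrasts use .0125. This stands. A reader might infer that every target-versus-sham statement lacks error control; the three-level design does not support that.

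**The .05 figures describe a less natural reading.** The threshold sentence stands unqualified in the neurostimulation paragraph, so .0125 for contrasts is the plainer reading. A reader might infer error rates of 40% or more, but the documents do not say that contrasts are judged at .05. What stands of the concern is that the scope is unstated and has to be settled in words.

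**The larger rates need particular truths.** An effect of 1.5 SD in one cell of 30, or a target that helps one group and harms the other, is not suggested by the documents. With run-level variance, which is plausible because each condition is its own run, the 0.5 SD one-cell rate is .013, essentially the allotment. This limits the size of the interaction problem. It does not touch the block-instruction result, though that result concerns instructions pooled over stimulation and not target versus sham.

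**The 20-contrast family is assumed.** This is true, and it follows from the plan naming no family. The interaction is stated only for SUDS and peak GSR, so the cell-level concern does not extend to SCL or HF-HRV as written.

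**Replacing everything with ungated Holm would do harm.** This also stands. If Holm over the 20 cells displaced the main-effect contrasts, a uniform 0.3 SD target effect would be found in about 10% of trials, against 81% with the gated main effect. Without the gate, one cell at 1.0 SD would lead to a claim despite a non-significant interaction in 41% of trials. That would loosen the plan after data collection.

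**Conclusion.** The concern holds for two families: the ten block-instruction pairs, and cell-level follow-up of the three-way interaction for SUDS and peak GSR. With contrasts at .0125, the first runs at about 6% when one level truly differs by 0.3 or 0.5 SD. Under the assumptions in the working, the second runs at 2/5/7/15% for a single shifted cell (0.5/0.8/1.0/1.5 SD) and 10/17/18% for a crossover (0.5/0.8/1.0 SD). Run-level variance lowers these rates, and they stay below 1% through the three-way gate when the effect does not differ by group. The exact rates depend on assumed effect sizes, covariance and the number of contrasts examined; two-way interaction gates were not simulated.

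It does not follow that the trial's target-versus-sham conclusions are generally unprotected. The omnibus gate works under no effects and for the stimulation main effect at .0125. This should be fixed, but the defect is confined to the post hoc step.

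**What to change.** 1. State that .0125 governs the marginal-mean contrasts as well as the omnibus tests.
2. Keep the omnibus gates. For every outcome, keep the gated active-versus-sham contrasts of the three-level stimulation main effect at .0125.
3. Behind a significant block-instruction effect, replace LSD with Holm over all ten pairs at .0125.
4. Behind a significant three-way interaction for SUDS or peak GSR, replace LSD with Holm over all 20 active-versus-sham contrasts within group and instruction at .0125. Because data collection ended before the document's date, use a smaller family only if it is documented as chosen before the data were seen.
5. Do not impose the cell-level family on SCL or HF-HRV unless that interaction is actually fitted and followed up.
6. State that each family is held at .0125 separately, so the total over main-effect and interaction families within an outcome can be somewhat higher. With Holm run ungated beside the gated main-effect contrasts, it was about .02.

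The cost is SAP wording, a re-run of the post hoc step and some power. With the gate kept, average power per true contrast falls from 22% to 19% for one cell at 1.0 SD, and from 64% to 31% for the crossover at 0.8 SD. For block pairs, with Holm simulated without the gate, it falls from 48% to 31% at 0.3 SD and from 97% to 91% at 0.5 SD. Some cell differences that are significant under LSD may no longer be so.

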Interested participants completed an online and in-person screen before being invited for an imaging session. We received completed ($n = 1120$) or partially completed ($n = 221$) online screens from 1341 potential unique participants (79.6% female, 9.2% Hispanic, 79.7% Caucasian). Of those who completed, 40.4% identified themselves as being interested in the study because they suspect having misophonia (MMQ_Subscale_1 = 2.56, $SD = 0.75$; MMQ_Subscale_2 = 2.39, $SD = 0.63$; MMQ_Severity = 7.78, $SD = 2.30$; MDERS = 96.30, $SD = 24.93$), and 44.3% because they believed they had emotional dysregulation (MMQ_Subscale_1 = 1.67, $SD = 0.84$; MMQ_Subscale_2 = 1.43, $SD = 0.73$; MMQ_Severity = 4.57, $SD = 2.62$; MDERS = 111.22, $SD = 21.84$). Of those who self-identified as misophonic, 38.56% met our inclusion criteria for the misophonia group; 9.60% of those self-identified as having emotional dysregulation also met inclusion criteria for the misophonic group. In addition, 39.48% of those who self-

identified as having misophonia, and 72.39% of those who self-identified as high emotional dysregulation were above the inclusion cutoff for the emotion dysregulation clinical group.

Three hundred and thirteen potential participants who qualified at online screen and who could be reached, were screened by phone to further examine study inclusion/exclusion criteria. Of these, 177 qualified and were invited to an in person intake assessment. Participants were excluded from either online or phone screen primarily for not meeting the cutoffs for either group, for being unreachable after completing the online screen, or for being unable to travel to Duke for the study appointments. Furthermore, 183 participants were rejected at screen because the misophonia group enrollment was completed much faster than the control group and, as a result, we were no longer accepting misophonic participants. One hundred and forty four additional participants reported high emotional dysregulation, but were excluded from the control group because they were considered to have too many misophonic symptoms. Participants were allowed in the control group only if the second MQ subscale < 2 and MQ severity score was < 7 . As a result, 23 potential controls were excluded because they had both subscale 2 and severity scale too high, 41 had the MQ severity score as too high, and 79 had subscale 2 score as too high.

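### The ROI–symptom correlations state no group term; if they are pooled and the groups differ in mean ROI signal, a correlation with MQ scores appears even when neither group shows a link

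*Combined protocol and SAP*

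**What the plan says.** Section 7 (Statistical Analyses) gives the analysis one sentence. To examine the brain basis of misophonia, "correlation analyses with neuroimaging data extracted from regions of interest (ROIs) and baseline behavioral measures were employed". It does not say whether the groups are pooled or analysed apart. It gives no coefficient, ROI list, list of measures or multiplicity rule for these correlations.

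Group is named elsewhere in Section 7. It is the comparison in the third-level imaging analyses and a factor in the SUDS, SCR, SCL and HF-HRV models. The covariates planned for all analyses are coil-to-cortex distance and data-driven additions; group is not among them.

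Section 1 defines the groups partly by cut-offs on one of the baseline measures. The Table 1 note says: "Participants were included in the misophonic group if they scored ≥ 2 on the MQ subscales and indicated a severity higher than 6". For controls: "Participants were allowed in the control group only if the second MQ subscale < 2 and MQ severity score was < 7". The scales were given again at intake ("We repeated the MQ and DERS at the in person screen and only" those still inside the cut-offs went on), and 22 people lost eligibility at that step.

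Section 1 also states the planning assumption for the group difference in anterior insular cortex (AIC) response, an effect size of 1.27.

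**The concern.** Subscale 2 cannot overlap between the groups, and severity cannot overlap if it is scored in whole points. MQ score is then close to a label for group. A correlation over all participants combines two things: the difference between the groups, and any relation between symptoms and signal among people in the same group. When the score is nearly a group label, the first part dominates.

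The stake is interpretation. A pooled coefficient reads as a graded relation (more symptoms, more signal) and could be offered as support for a mechanism, when the data may hold only a difference between two selected groups. The third-level imaging analysis already tests that difference directly.

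**Working it through.** **The plan's own figure.** No figure is given for the correlations. The planning effect size reproduces: 2.7 / 2.11 = 1.28, against the stated 1.27.

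**Formula.** For two equal groups with zero correlation inside each, pooled r = r(group, MQ) × r(group, ROI), where r(group, ·) = d / √(d² + 4).

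**ROI side.** At d = 1.27: 1.27 / √(1.6129 + 4) = .536.

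**MQ separation before selection.** Section 1 gives severity means (SD) for self-identified screeners of 7.78 (2.30) and 4.57 (2.62).
- Pooled SD = √((2.30² + 2.62²)/2) = 2.465, so d = 3.21 / 2.465 = 1.30 and r(group, MQ) = .546.
- Pooled r = .546 × .536 = .29. At n = 59 enrolled, t = 2.31 on 57 df, p = .025.

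**MQ separation after selection.** MQ means for the enrolled sample are not given, so this step is an assumption: normal scores with the screening means and SDs, truncated at the entry cut-offs.
- Severity becomes 8.88 (SD 1.62) and 3.89 (SD 1.56), so d = 3.14 and r(group, MQ) = .843. Subscale 2 gives d = 3.15.
- Pooled r = .843 × .536 = .45.

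**Simulation.** 20,000 replicates, 27 per group (the completers), truncated severity scores, ROI signal independent of MQ inside each group, two-sided α = .05:

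| ROI group difference d | Mean pooled r | Pooled r significant | Mean group-adjusted r | Adjusted r significant |
|---|---|---|---|---|
| 0 | .00 | 5% | .00 | 5% |
| 0.2 | .09 | 9% | .00 | 5% |
| 0.5 | .21 | 33% | .00 | 5% |
| 0.8 | .32 | 67% | .00 | 5% |
| 1.27 | .46 | 96% | .00 | 5% |

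Subscale 2 agrees to within about one percentage point. At .0125, the Bonferroni level that Section 7 sets for the four neurostimulation analyses, the last row would still be significant about 88% of the time.

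**A measure that does not define both groups.** Screening DERS means (SD) are 96.30 (24.93) and 111.22 (21.84).
- Pooled SD = 23.44, so |d| = 14.92 / 23.44 = .64 and r(group, DERS) = .303 in size.
- Induced |r| = .303 × .536 = .16, p = .22 at n = 59.
- These means precede selection. Truncating the control side at its DERS floor of 89 gives a mean of 117.3 (SD 17.3). Then |d| = 21.0 / 21.4 = .98 and |r| = .440 × .536 = .24, p = .07. That is still about half the MQ value.

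**Cost of adjustment.** The share of MQ variance inside groups is 1 − .843² = .29. At the same residual SD, the standard error of the within-group slope is 1/√.29 = 1.9 times that of the pooled slope.

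**The case against.** Four points on the other side have weight.

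- **Pooling is not stated.** The text is silent and neither excludes within-group nor partial correlations. Section 5 says that the complete fMRI analyses will be reported elsewhere. This stands. But the choice decides what the result means, and group is named in the other models and not here.
- **Selection alone does no harm.** A reader might infer that choosing groups far apart on the MQ produces a correlation by itself. It does not: with equal ROI means the average pooled r is zero and the error rate stays at 5%. The condition is a difference in ROI means. The study was powered on such a difference in the AIC, but no figure is given for the dlPFC or vmPFC, and the size falls with the difference. At ROI d = 0.8 and the pre-selection MQ separation, r = .371 × .546 = .20, p = .12 at n = 59.
- **Most baseline measures are not the MQ.** A reader might extend the point to every questionnaire. The entry rules set the groups apart on MQ subscale 2 and severity. The Table 1 note sets a DERS floor for the dysregulation group only, and the induced correlation there is small.
- **The within-group slope is not the only legitimate test.** Group is itself cut from the MQ, so a group term removes a coarse version of the predictor. If misophonia is dimensional, the between-group difference is part of the true relation, and the less precise within-group slope could miss a real link. This stands, and is why both estimates should be shown.

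The documents contain no dose-response claim, and these correlations are not among the listed primary or secondary outcomes. The risk lies in how the result would be read.

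**Conclusion.** The concern holds in conditional form. If the correlations are pooled and the groups differ in mean ROI signal, a correlation with MQ scores arises without any link inside either group. At the planning AIC difference it is about .29 at the pre-selection MQ separation and about .46 at the separation implied by the cut-offs. The larger value would be significant about 96% of the time with 27 per group.

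These sizes rest on equal groups, equal ROI SDs, two-sided tests and, for the larger value, truncated normal MQ scores based on screening data. The documents do not support saying that the plan does pool, that the artefact arises with equal ROI means, or that it is material for baseline measures in general. Other misophonia-severity scales (AMISOS-R, DMQ) probably behave like the MQ, but the documents give no group values for them.

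This is more than a missing detail. The sentence as written permits an analysis that cannot separate a symptom relation from a group difference, and a better one is available from the same data.

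**What to change.** State whether the ROI–symptom correlations are pooled, stratified or adjusted. For the MQ and other misophonia-severity measures:

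- Fit ROI signal on group and symptom score, and report the within-group or group-adjusted slope with its interval. Show the group-by-score term.
- Place this beside any pooled correlation, and label the pooled value as not separable from the group difference.
- Claim a graded symptom–brain relation only if the within-group estimate supports it.

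For the DERS and similar measures the same layout is good practice but less pressing.

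The change needs no new data: one model term plus the interaction. The cost is precision. With about 30% of MQ variance inside groups, the slope's standard error is roughly 1.9 times the pooled one. A wide within-group interval should therefore be reported as inconclusive, not as evidence that no relation exists.
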